Study design	Multi-site, prospective observational cohort study.
Study Aim and Objectives	
Aim: To establish the feasibility and acceptability of implementing Speech Recognition Application for the Voice Impaired (SRAVI) for acute and critical care patients with a tracheostomy who are unable to communicate using verbal speech.
 
Objectives:
 
 1. To evaluate patients' capability in using SRAVI and barriers to its use. 2. To measure accuracy of SRAVI. 3. To explore the experience of patients, their significant others, and acute and critical care multidisciplinary team (MDT) members with and without the use of SRAVI. 4. To assess recruitment and collection of clinical outcomes.
Study Intervention	Speech Recognition Application for the Voice Impaired (SRAVI)
Comparator	None
Primary outcome	
 1. Patient capability to use SRAVI 2. User acceptability of the intervention
Secondary outcomes	
 1. Feasibility of collection of clinical data measures: 
 a. Duration of critical care length of stay b. Duration of hospital length of stay c. Delirium occurrence during critical care stay d. Health Related Quality of Life (HRQoL) e. Anxiety and depression f. Post-Traumatic Stress Disorder (PTSD) g. Cognitive status 2. Estimation of recruitment and retention to inform design of a clinical trial. 3. Identification of additional important outcomes reported by patients, relatives, and healthcare professionals.
Key inclusion and exclusion criteria	
Patient inclusion criteria:
 
 1. Patients aged 18 years and over 2. Patients who acquire a tracheostomy in acute or critical care

	
3. Patients can move lips in a way that articulates words 4. Able to communicate in English (a current requirement of the technology)
 
Patient exclusion criteria:
 
 1. Patient declined consent
Study setting	Three critical care units in Northern Ireland: Royal Victoria Hospital (RVH), Belfast; City Hospital, Belfast and Altnagelvin Hospital, Derry and a regional head and neck centre, RVH Belfast.
Sample size	A minimum target of 55 patients.
Study Duration	18 months

STUDY TEAM

Chief Investigator	[name] Wellcome-Wolfson Institute for Experimental Medicine, Queen's University Belfast (QUB)

1. BACKGROUND AND RATIONALE

1.1 Background Information

Voice represents one of the most fundamental components of human communication. Yet when patients are admitted to hospital their ability to effectively communicate may be temporarily or permanently compromised by the nature of their illness and treatment.

Critical Care

In the UK, approximately 10,000 patients annually undergo a tracheostomy (1). A paradigm shift in critical care management towards lighter sedation in mechanically ventilated patients has increased the number of patients potentially able to communicate while awake (2). An advantage of tracheostomy is that patients can have reductions or cessation of sedative medication but may find themselves in a situation where they are alert, yet still reliant on positive pressure ventilator support. This almost universally requires an inflated tracheostomy tube cuff to deliver the pressure generated by the ventilator to the lungs. For the majority of these patients who remain significantly ventilator-dependent or have a considerable aspiration risk that inhibits cuff deflation, the continued presence of the inflated cuff by necessity 'seals off' the upper airway, preventing effective oral communication (3).

The impact of altered communication function has been described as one of the most stressful events of critical care admission (4) and the presence of a tracheostomy tube with an inflated cuff significantly impacts upon an individual's ability to effectively communicate, interact, and participate within the healthcare system (5). Nearly two-thirds of ventilated patients report communication as difficult, and this contributes to negative emotions during critical care (6,7). Patients report loss of voice leading directly to frustration (8), panic (9), anger (10), fear (11), a sense of depersonalisation, powerlessness, and a sense of futility (12, 13). Importantly emotional distress experienced during critical care is a predictor of negative psychological outcomes during recovery. Anxiety (14, 15), depression (16, 17), PTSD (18, 19) and intrusive and delusional memories (20, 21) have been reported as frequent sequelae for many critical care survivors. Delirium, a form of acute brain dysfunction that is common during critical illness, has consistently been

shown to be associated with long-term cognitive impairment. Impaired communication may contribute to delirium. Cognitive dysfunction following critical care discharge has been demonstrated in up to 66% of survivors, with impairments documented in one-third up to six years after hospital discharge (22).

Acute Care

In the UK approximately 12,400 new cases of head and neck cancer are diagnosed annually. Accounting for 3% of all new cancer cases, it is the 8th most common cancer in the UK (23). For some patients with laryngeal carcinoma, total laryngectomy is a treatment option (24). This surgical procedure involves the disconnection of the airway following removal of laryngeal structures and part of the upper trachea. Although an effective cancer treatment, the resulting permanent tracheostomy is at the expense of the patient's natural voice (25). Whilst many patients adapt well to new forms of communication, some experience considerable psychosocial burden. Greater levels of depression and anxiety have been reported in 30% of TL patients (26). Loss of natural voice is also associated with decreased social activity with an estimated 40% of patients experiencing social withdrawal (27).

In addition to laryngectomy (a planned procedure resulting in a permanent tracheostomy), various scenarios in the acute care setting may necessitate a temporary tracheostomy. Reasons may include upper airway obstruction resulting from conditions such as vocal cord paralysis, tracheal or laryngeal stenosis, infection, or trauma. A tracheostomy establishes an alternative pathway for air to bypass the upper airway, thereby facilitating its passage into the lungs.

1.2 Rationale for the study

Augmentative and Alternative Communication (AAC) strategies describe a wide spectrum of tools, technologies, and/or approaches used to solve communicative challenges in patients who are unable to communicate through verbal speech (28).

Critical Care

AAC is not always effective in the critical care setting as strategies for voiceless patients are often too complex for this population. Critical illness neuropathy and

altered cognitive functioning often mean that patients lack the manual dexterity to use such aids (29). Low-tech communication aids including pen and paper and communication boards have been described as tedious, limited, and slow (30) whilst high-tech aids such as eye-gazing systems use bespoke hardware and require significant patient learning (31). Although one-way speaking valves have been successfully used to restore audible and meaningful speech in patients after tracheostomy placement (32-33), criteria for selection of candidates for use includes the ability to tolerate tracheostomy cuff deflation. Above Cuff Vocalisation (ACV) may be helpful for those patients who cannot tolerate cuff deflation as this technique uses the subglottic suction port of the tracheostomy tube to deliver a low flow of air or oxygen backwards up the port to exit above the cuff (34). Gas flow can then travel upwards through the trachea, pass through the vocal cords, and exit via the mouth, resulting in audible vocalisation. However, this is a relatively new technique with numerous contraindications and requires further research (35). There is a need to develop more effective AAC strategies for critical care patients.

Unaided modalities such as silent articulation of speech, gesturing, and body language remain the primary mode of communication used by critical care tracheostomy patients despite evidence showing that they are frustrating, insufficient, and characterised by patients not being understood (36-37). The inability to accurately interpret what patients are trying to say also frequently results in staff experiencing feelings of incompetence and despair (38-39). Studies have described typical communication between patients and healthcare professionals as brief and targeting primarily basic medical needs due to the difficulty in understanding what the patient wishes to say (40). Critical care patients describe their needs as multi-dimensional (41) and have highlighted the need for easy to use and intuitive communication aids (42-43). Impaired communication can prevent non-vocal tracheostomy patients from not only expressing their needs and symptoms but also emotions, and from participating in decisions regarding their own treatment (44). The integration of reliable communication interventions at the bedside is essential to decreasing the challenges and vulnerabilities experienced by critical care patients recovering from events resulting in sudden speechlessness.

Whilst recent years has seen significant advances in voice restoration techniques following total laryngectomy, in the immediate postoperative period, low-tech strategies including writing and communication boards are frequently utilised. Alternative options such as oesophageal speech or electrolarynx speech are often difficult to learn effectively (45). Tracheo-Esophageal Speech (TE-speech), a voice prosthesis, may also be utilised but successful TE-speech is not guaranteed with outcomes in voice quality and intelligibility differing between patients (46).

For patients in acute care undergoing emergency tracheostomy, communication strategies closely resemble those used in critical care settings and the immediate postoperative period for total laryngectomy patients.

1.3 Rationale for the intervention

Speech Recognition Application for the Voice Impaired (SRAVI) is a novel communication aid developed by Liopa (a company formed by Queen's University Belfast (QUB) and the Centre for Security Information Technologies (CSIT), QUB). SRAVI is an application-based lip-reading system, and the application ('app') can be downloaded onto any device with a standard forward facing camera (e.g., smartphone, tablet). When the device is held in front of a patient, it will track lip movement and identify phrases being mouthed (Figure 1).

[figure not shown]

Figure 1: SRAVI application (47)

SRAVI has been in trial by the Lancashire Teaching Hospitals NHS Foundation Trust since 2019. The phase 1 trial included 15 patients who had lost their ability to speak from having tracheostomies and 33 critical care staff members (48). During this initial phase, rapid cycles of testing confirmed that SRAVI can be used to communicate from a list of the most common and important phrases as identified by patients and staff with

good accuracy. As SRAVI is based upon artificial intelligence (AI) algorithms, it was important to determine that the app will read the patients' lips better as they continue using it. Critically, Phase I proved that SRAVI returns the correct phrase that has been lip-read with greater than 90% accuracy. The recognition system is able to discern the correct phrase in the top 3 with 100% accuracy. The longer the patients used SRAVI, the better the app became at interpreting what they were saying (Figure 2).

[figure not shown]

Figure 2: Accuracy and SRAVI engagement (49)

Compared to the limited alternatives available, SRAVI potentially could provide an easier, more accurate, and cost-effective method for communication between tracheostomy patients, healthcare professionals, and relatives.

2. RESEARCH AIM AND OBJECTIVES

2.1 Research Aim

The overarching aim of this research is to establish the feasibility and acceptability of SRAVI for adult acute and critical care patients with a tracheostomy who are unable to communicate using verbal speech.

2.2 Research Objectives

1. To evaluate patients' capability in using SRAVI and barriers to its use.
2. To measure accuracy of SRAVI.
3. To explore the experience of patients, their significant others, and acute and critical care multidisciplinary team (MDT) members with and without the use of SRAVI.
4. To assess recruitment and collection of clinical outcomes.

3. STUDY DESIGN AND SETTING

3.1 Study Design

This is a mixed-method, multi-centre prospective observational cohort study to establish the feasibility of SRAVI. Mixed methods include:

- A multi-centre prospective observational cohort study of SRAVI as an addition to usual communication aids.
- Qualitative interviews to inform future study design by exploring patients', their significant others and the acute and critical care MDTs' subjective experiences of the study intervention and outcome measures.

3.2 Study Setting

The study will be conducted at four sites: the 32- bed regional critical care unit based at the Royal Victoria Hospital (RVH), Belfast, NI; the 10- bed general critical care unit based at the City Hospital, Belfast, the 10-bed general critical care unit based at Altnagelvin Hospital, Derry, NI and a regional head and neck centre based at RVH Belfast

3.3 Sample Size

The sample size is based on previous critical care feasibility studies showing a participation rate of 50%. Due to the onset of the SARS-CoV-2 pandemic, the role and timing of tracheostomy for patients requiring critical care for coronavirus disease (COVID-19) remains unclear (50). To circumvent this, pre-COVID19 local audit data has been used to estimate sample size. In 2019, an average of 70 tracheostomies were completed in Royal Victoria Hospital, Belfast, 20 in City Hospital, Belfast and 20

in Altnagelvin Hospital, Derry. We aim to recruit as many patients as possible but aiming for a minimum target of 55 patients.

For every patient recruited to the prospective observational cohort study, we will aim to undertake two interviews as part of the qualitative component of the study (i.e., the patient and their significant other). We will also aim to host a minimum of five staff focus groups and will include a representative sample of medical, nursing and allied healthcare professionals of various grades with no more than eight participants per session.

Therefore, a feasible target recruitment is 150 participants. However, in keeping with the principles of rigorous qualitative research we will be responsive to the study context and anticipate that in some cases fewer interviews/focus groups will be conducted and in others, additional interviews/focus groups will be conducted to achieve data saturation.

[figure not shown]
3.4 Duration of study

The proposed study duration is 18 months.

- **Recruitment phase:** patient recruitment is estimated to take 14 months.
- **Treatment phase:** SRAVI in addition to usual communication aids will be used for the duration of the patient's acute or critical care stay.
- **Follow-up phase:** 3 months after acute or critical care discharge.
- **End of study:** is defined as the last 3-month observation of the last patient in the follow-up phase of the study and is anticipated to be 17 months after recruitment of the first patient.

3.5

Study schematic diagram

3.6 Primary Outcome Measure

1. Capability of patients to use SRAVI as defined by:
 - Measurement of frequency of use.
 - Measurement of words correctly captured.
 - Measurement of frequency of patients who could not use SRAVI and reverted to other communication aids.
2. Acceptability of SRAVI as a communication aid as expressed in qualitative interviews with patients, family and the MDT.

3.7 Secondary Outcome Measures

1. Enrolment: the ability to identify eligible patients over the study period.
2. Consent: the number of patients consenting to be included as a proportion of all patients approached about the study, with reasons for non-consent.
3. Retention and dropout rates:
 - Number of patients who commence the intervention as a proportion of the number recruited, with reasons for non-compliance.
 - Number of patients who continue the intervention as a proportion of the number recruited, with reasons for non-continuation.
 - Qualitative assessment of barriers/facilitators to data collection and participant retention
4. Data collection of outcome measures:
 - I. Duration of critical care length of stay
 - II. Duration of hospital length of stay
 - III. Delirium occurrence during critical care stay (delirium positive on CAM-ICU)
 - IV. Clinical outcomes at 3-months post-critical care discharge
 - a. Health related Quality of Life measured by the European Quality of Life-5 Dimensions (EQoL-5D)
 - b. Anxiety and depression measured by the Hospital Anxiety and Depression Scale (HADS).
 - c. Posttraumatic stress measures by the Impact of Events Scale-Revised (IES-R).
 - d. Cognitive status measured by the Montreal Cognitive Assessment-BLIND (MOCA-BLIND).
5. Identification of additional important outcomes (by qualitative interviews).

3.8 Study Intervention

All consenting participants will receive access to SRAVI, a communication aid for speech-impaired patients. SRAVI is a software-based mobile application ('app') and can be downloaded onto any device with a standard forward facing camera (e.g., smartphone, tablet). SRAVI has been registered with the Medical and Healthcare

products Regulatory Agency (MHRA) and CE marked for intended use. SRAVI is based on LipRead, Liopa's Visual Speech Recognition (VSR) platform. Specifically, the LipRead technology can determine speech by analysing the movements of a user's lips as they speak into a camera. These lip movements are known as visemes and are the visual equivalent of a phoneme or unit of sound in spoken language.

A flow chart showing how the video data is passed through the system is shown in Figure 3. Using the device camera, SRAVI records a video of the patient mouthing a phrase. The patient's ID is entered by the device user. The video file is stored in an archive with restricted access. A record of users and phrases is stored anonymously in a database. This video is sent to a secure server with data encrypted at rest and during transit, meaning that the data cannot be viewed by any third parties. Video clips will be retained for the lifetime of the study to enable Liopa to improve the system over time and to run all data through at the conclusion of the study to provide updated accuracy results. Once the video reaches the server, LipRead technology detects and tracks the lip movements and converts those into text on the device screen within a few seconds (Figure 3). SRAVI can adapt to an individual's lip movements over time, which means it becomes increasingly accurate the more it is used.

[figure not shown]

Figure 3: How SRAVI works (51)

4. Screening, recruitment, and consent

4.1 Eligibility Criteria

All patients admitted to the acute and critical care facilities during the study period and fulfilling the following inclusion criteria will be eligible.

4.1.1 Inclusion Criteria

- Patients aged 18 years and over at the time of screening
- Have a tracheostomy in-situ that was inserted during current acute or critical care admission
- Able to communicate in English (a current requirement of the technology)
- Able to move lips in a way that articulates words

4.1.2 Exclusion Criteria

- Patient declined consent

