4.2 Recruitment and Screening Procedure

The research fellow will consult members of the acute and critical care team at each study site daily to establish the eligibility of acute and critical care tracheotomised patients. All patients who meet all the inclusion criteria and none of the exclusion criteria will be eligible for inclusion in data analysis. Authorised nursing/medical staff on the delegation log will confirm eligibility. A screening log will be maintained that will include details of the number of participants excluded and the reason for exclusion.

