5.3 Data Analysis

Descriptive analysis will be used to analyse data from the prospective observational cohort study. Numbers of patients screened, eligible, recruited, consented, and withdrawn from the study will be reported. Baseline demographic and clinical data will be summarised for study participants. Continuous variables will be summarised as mean (standard deviation) and median (interquartile range) and categorical variables will be summarised as number (percent).

Twenty five percent of all data variables collected by the research fellow during baseline, intervention and follow-up phases of this study will be independently

reviewed by another clinician using the baseline, intervention, follow up and quality of life proformas devised for this study.

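### Sections 4.1 and 4.2 disagree on who counts as eligible, because refusal of consent is listed as the only exclusion criterion; patients who decline can drop out of the reported eligible count.

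*Combined protocol and SAP*

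**What the plan says.** Section 4.1 makes eligible all patients admitted in the study period and "fulfilling the following inclusion criteria will be eligible". It does not mention exclusions. Section 4.1.2 then lists one exclusion criterion, "Patient declined consent", which the Protocol Summary repeats.

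Section 4.2 states: "All patients who meet all the inclusion criteria and none of the exclusion criteria will be eligible for inclusion in data analysis". It adds: "A screening log will be maintained that will include details of the number of participants excluded and the reason for exclusion".

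Three places use or report recruitment flow:

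- Section 3.7, first secondary outcome: "Enrolment: the ability to identify eligible patients over the study period". No formula or denominator is given.
- Section 3.7, second secondary outcome: "the number of patients consenting to be included as a proportion of all patients approached about the study, with reasons for non-consent".
- Section 5.3: "Numbers of patients screened, eligible, recruited, consented, and withdrawn from the study will be reported".

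The Protocol Summary says that the recruitment and retention estimates are meant to inform the design of a clinical trial. Section 3.3 bases the sample size on "previous critical care feasibility studies showing a participation rate of 50" per cent.

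**The concern.** Declining consent is something that happens during recruitment. It is not a characteristic that makes a patient unsuitable for the study. Once it is listed as an exclusion criterion, a site that applies section 4.2 literally would log an approached patient who refuses as excluded, while an eligible patient who was never approached remains eligible. The reported eligible count would then hold recruited and unapproached patients but no patient refusals.

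In a feasibility study this count is a result in its own right. A recruited/eligible ratio built on the reduced count would be too high, and a later trial planned on it would look for too few eligible patients. The consented/approached rate cannot take its place, because it says nothing about eligible patients who were never approached.

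Two side effects follow from the same wording. The criterion names only the patient, so negative advice from a consultee does not trigger it, although section 4.3.2 expects consultee advice to be the usual route in critical care. And section 4.3.4 lets a patient who refuses after regaining capacity allow use of data already collected, whereas sections 4.1.2 and 4.2 read literally would bar that patient from the analysis.

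**Working it through.** **1. The two rules side by side.**

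| Patient (meets 4.1.1) | Eligible under 4.1 | Meets the condition in 4.2 |
|---|---|---|
| Recruited | yes | yes |
| Never approached | yes | yes |
| Patient declined | yes | no |
| Consultee advised against | yes | yes (not named in 4.1.2) |
| Refused after regaining capacity, allows use of earlier data | yes | no, although 4.3.4 admits the data |

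The rules differ in the third and fifth rows. Section 5.3 does not say which one feeds its eligible count.

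**2. Inputs (section 3.3).** Tracheostomies in 2019 at the three hospitals: 70, 20 and 20. Participation: 50%. Minimum target: 55.

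**3. The plan's own figure.** 70 + 20 + 20 = 110, and 110 × 0.50 = 55. The stated target is reproduced.

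**4. Effect of removing patient decliners.** Assume that all 110 meet section 4.1.1. Then 55 are recruited and 110 − 55 = 55 are not. Let s be the share of those 55 non-participants who are patient decliners. The documents do not give s, so it is varied from 0 to 1.

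- Eligible count without decliners: E(s) = 110 − 55s
- Understatement: 55s / 110 = 0.5s
- Recruited/eligible: 55 / (110 − 55s)

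| s | Decliners removed | E(s) | Understatement | Recruited/eligible |
|---|---|---|---|---|
| 0 | 0 | 110 | 0% | 50% |
| 0.25 | 13.75 | 96.25 | 12.5% | 57.1% |
| 0.5 | 27.5 | 82.5 | 25% | 66.7% |
| 0.75 | 41.25 | 68.75 | 37.5% | 80% |
| 1 | 55 | 55 | 50% | 100% |

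(The fractions are expected counts.)

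**5. After the fix.** With decliners kept in, the eligible count is E(s) + 55s = 110 and recruited/eligible is 55/110 = 50% for every s.

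**6. What does not move.** Consented/approached has the same numerator and denominator under either rule. The target of 55 comes from step 3 and does not use the eligible count.

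**7. Consequence for a later trial.** To recruit N patients at a true ratio of 50%, N / 0.50 = 2N eligible patients are needed. Planning at the extreme ratio of 100% would give N, half of what is needed.

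**The case against.** A reader might infer that the plan makes every decliner ineligible, so that the eligible count is simply wrong, by half. The documents do not support that, for these reasons.

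- **Section 4.1 already gives the right definition.** It uses the inclusion criteria alone, so decliners stay eligible. The condition in section 4.2 concerns whose data are analysed, and a patient who refuses at the outset would contribute none anyway.
- **The sequence favours section 4.1.** Staff establish and confirm eligibility first. Under sections 4.3.2 and 4.3.6 the approach follows screening, so eligibility is settled before anyone can decline.
- **The information is partly recoverable.** The screening log holds reasons for exclusion, reasons for non-consent are an outcome, and section 5.3 lists eligible and consented as separate counts. Patient refusals logged as such can be added back.
- **No recruited/eligible ratio is prespecified.** The plan defines consented/approached, which is sound. Enrolment has no formula, and the recruitment rates in section 5.1.3 have no denominator.
- **The 50% figure is a ceiling.** It needs every non-participant to be a patient decliner. In critical care many negative answers would come from consultees, whom the criterion does not name. Nor are all 110 tracheostomies certain to meet section 4.1.1.

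All of this stands, and it limits the point to an ambiguity. It does not remove it. Two rules remain, the plan does not choose between them for the section 5.3 count, and four sites could log differently. Adding refusals back is a repair that the plan does not specify. The log as described has no category for patients not approached or for consultee refusals. The conflict with section 4.3.4 is untouched by these arguments.

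**Conclusion.** The point holds as an inconsistency between sections 4.1 and 4.2 that can bias a stated feasibility result. It does not show that the eligible count will be wrong. If sites follow section 4.1, nothing is lost. If they follow section 4.2 literally, the eligible count is understated by 0% to 50% and recruited/eligible reads 50% to 100% instead of 50%.

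That range rests on three things: the 2019 total of 110 with 50% participation, the assumption that all 110 meet section 4.1.1, and a share of patient decliners that the documents do not give. The direction is certain wherever any decliner is removed: the eligible count falls and the ratio rises. The consented/approached rate and the target of 55 stand. Sections 4.1.2 and 4.2 must also be reconciled with section 4.3.4 on data collected before a refusal. The correction is worth making because it is nearly free and protects figures meant to inform a trial.

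**What to change.** 1. Delete the refusal criterion from section 4.1.2 and from the Protocol Summary.
2. State in section 5.3 that the eligible count means patients who meet all the inclusion criteria, whether or not they are approached or agree.
3. Add a rule for laryngectomy patients. Under section 4.3.5 they are informed before surgery and asked on admission for it, when the tracheostomy that section 4.1.1 requires is not yet in place. Count those expected to meet the criteria after surgery. Otherwise those who decline at that point would still be missed.
4. In the screening log use three categories: *eligible, not approached*; *eligible, declined (patient or consultee, with reason)*; *eligible, recruited*.
5. Report recruited/eligible beside consented/approached, with both denominators defined.
6. Reword section 4.2 so that inclusion in the analysis depends on consent or consultee advice and agrees with section 4.3.4.

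The cost is one line deleted in two places, a few reworded sentences and one log column. The only downside is that reported uptake may look less favourable.
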